### **2.2 Secondary Objectives**

221 To determine the effect of eltrombopag on megakaryopoiesis - median time to reach platelet count  $\geq 50,000 / \mu$ L and  $\geq 100,000 / \mu$ L, number of days of platelet transfusion, rates of platelet transfusion-independence and the median time to reach platelet transfusion-independence.

222 To determine the effect of eltrombopag on the rates of clinically significant bleeding events (CSBE) [Appendix I].

223 To determine the effect of eltrombopag on erythropoiesis the median time to red blood cell transfusion independence.

224 To determine the effect of eltrombopag on granulopoiesis- the time taken to reach an absolute neutrophil count of  $\geq 500 / \mu$ L.

225 To determine the safety and tolerability of eltrombopag in AML patients undergoing remission IC - incidence and severity of eltrombopag-related adverse events.

226 To determine the rates of CR, rates of CRp, time to attain CR, and time to initiation of postremission therapy.

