## **4.0 STUDY DESIGN**

### **4.1 Overall Design**

This is a single institution, single arm, non-randomized phase II clinical trial with a sample size of 31 patients. The primary goal of this trial is to determine if eltrombopag can accelerate platelet count recovery in older AML patients (age  $\geq$ 60 years) who have no morphological evidence of leukemia in the bone marrow following remission IC. The standard remission IC for AML in patients  $\geq$ 60 years will consist of an anthracycline (daunorubicin or idarubicin) for 3 days and cytarabine as continuous intravenous infusion for 7 days. The patients in the study will receive supportive blood transfusions as part of standard of care at the Cleveland Clinic. Use of erythropoiesis stimulating agents (ESA) or granulocyte colony stimulating factors (G-CSF) during or following remission IC is not permitted. The study schema is shown below.

In those patients who have no morphologic evidence of disease on day 14 (range, 14-17) bone marrow evaluation, eltrombopag will be administered within 5 business days from the date of day 14 (range, 14-17) bone marrow biopsy. There will be a gap of at least one week (range, 7-9 days) between the last day of remission IC and initiation of eltrombopag, which will allow sufficient time for complete washout of the chemotherapeutic agents. Dose modification will be determined based on platelet counts and presence of adverse event(s).

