**3) Kinetics of erythrocytic recovery:** Parameters to be assessed will include the median number of days needed to reach a hemoglobin level  $> 8\text{ g/dl}$  (first of the 5 consecutive days with hemoglobin  $> 8\text{ g/dl}$ ) starting from the first day of study drug administration, maximal rise in hemoglobin level after achieving transfusion-independence and rates of red blood cell transfusion-independence within 4 weeks of IC. An erythroid response in patients with a pretreatment hemoglobin level of  $< 8\text{ g/dL}$  (transfusion-dependent) will be defined as an increase in the hemoglobin level by  $1.5\text{ g/dL}$  or more without transfusion of packed red cells that is sustained for at least 2 weeks (from the start date of eltrombopag) or a 50% reduction in the number of units of packed red cells transfused in the 2 consecutive weeks following eltrombopag use compared to the transfusion requirement in the 2 weeks preceding use of the study drug.

**4) Characterization of platelet response to eltrombopag by AML subtype (WHO classification), etiology of AML (*de novo* versus secondary) and cytogenetic risk groups.**

**5) Treatment/Disease outcomes:** CR rates, time to attain CR, CRp rates, time to initiation of post-remission therapy, rates of refractory or persistent disease, survival and safety profile.

Safety will be evaluated from the incidence and severity of adverse events based on clinical assessment and laboratory evaluations, determined according to the Common Terminology Criteria for Adverse Events (CTCAE), version 4.0 of the National Cancer Institute (NCI) Cancer Therapy Evaluation Program (CTEP). Survival will be calculated from the day of study enrollment until the last follow-up or death. Disease-free survival will be calculated from the date of complete remission until relapse, the date of last follow-up, or death.

Response criteria of AML patients to IC will be based on AML International Working Group (IWG) criteria (**Appendix III**). Modified AML response criteria include: morphologic leukemia free state, morphologic CR, cytogenetic CR, molecular CR and CRp. IWG criteria do not require presence of bone marrow cellularity (usually profoundly hypocellular from the effects of cytotoxic chemotherapy) or absence of dysplasia as a criterion for remission status.

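### The objective of time to red-cell transfusion independence has no endpoint or definition in section 10.2, and the hemoglobin time listed there can be met by transfusion alone

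*Combined protocol and SAP*

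**What the plan says.** Section 2.2 gives one erythroid measure, in objective 2.2.3: "the median time to red blood cell transfusion independence".

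Section 10.2, item 3 (erythrocytic recovery), lists four:

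- "the median number of days needed to reach a hemoglobin level" above 8 g/dL, taken as the first of 5 consecutive days;
- the largest hemoglobin rise once independence is reached. The text linking these two reads "starting from the first day of study drug administration, maximal rise in hemoglobin level after achieving transfusion-independence";
- "rates of red blood cell transfusion-independence within 4 weeks of IC";
- an erythroid response for patients with pretreatment hemoglobin below 8 g/dL, a group the section labels transfusion-dependent. One limb needs a rise of 1.5 g/dL "or more without transfusion of packed red cells that is sustained for at least 2 weeks". The other needs "a 50% reduction in the number of units of packed red cells transfused in the 2 consecutive weeks following eltrombopag use".

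Section 4.1 states: "The patients in the study will receive supportive blood transfusions as part of standard of care". Section 5.10.6 refers to institutional guidelines. Neither gives a hemoglobin trigger or a number of units.

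Section 12 names platelet transfusion independence and the effect on hemoglobin among its secondary goals. It does not name red-cell transfusion independence. It assigns Kaplan-Meier summaries to time-to-event data in general.

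**The concern.** There are two separate gaps. First, the one quantity the erythroid objective asks for is a time to independence, and the endpoint section offers a rate instead. Independence itself is undefined, so neither the rate nor the rise after independence can be computed without a choice made after the data are seen.

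Second, the only erythroid time that is defined ignores transfusion. These patients have just had intensive chemotherapy and receive red cells as standard care. A hemoglobin above 8 g/dL for five days may reflect the marrow or the blood bank, and the rule does not distinguish them. In a single-arm trial no control group would show the difference, so heavier transfusion could be reported as faster erythroid recovery.

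**Working it through.** There is no stated figure to reproduce. The check compares the rules and then asks whether transfusion alone can satisfy the hemoglobin rule.

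**Rules side by side (section 10.2)**

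| | Platelets (item 1) | Red cells (item 3) |
|---|---|---|
| Time to transfusion independence listed | Yes | No |
| Independence defined | Yes, 5 consecutive days at or above 50,000/µL | No |
| Clock starts | IC day 1 | First study drug (hemoglobin time) |
| Days must be untransfused | Yes | Not for the hemoglobin time; yes for one limb of the erythroid response |
| Censoring stated | Yes, last day of study | No |

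**Can transfusion alone meet the hemoglobin rule?**

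All inputs here are assumptions for illustration, not values from the documents: no red-cell production; hemoglobin falls by d = 0.10 to 0.20 g/dL per day; each unit adds 1 g/dL; transfusion of 1 or 2 units on the day hemoglobin is below a trigger of 7.0, 7.5 or 8.0 g/dL; that day's count is taken after transfusion.

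To stay above 8 for five days, hemoglobin on the first of them must exceed 8 + 4d: 8.4 (d = 0.10), 8.6 (0.15) or 8.8 (0.20). In a repeating cycle, hemoglobin after transfusion lies between trigger − d + units and just under trigger + units.

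| Trigger | Units | Hemoglobin after transfusion | Five days above 8? |
|---|---|---|---|
| 7.0 | 1 | 7.8 to <8.0 | Never |
| 7.0 | 2 | 8.8 to <9.0 | Yes, except exactly at 8.8 when d = 0.20 |
| 7.5 | 1 | 8.3 to <8.5 | Only at d = 0.10, and only above 8.4 |
| 7.5 | 2 | 9.3 to <9.5 | Yes |
| 8.0 | 1 | 8.8 to <9.0 | Yes, except exactly at 8.8 when d = 0.20 |
| 8.0 | 2 | 9.8 to <10.0 | Yes |

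One patient, starting at 7.8 g/dL with d = 0.15:

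- Trigger 8.0, 1 unit: transfused on day 1, then 8.80, 8.65, 8.50, 8.35, 8.20. Recorded time: day 1.
- Trigger 7.0, 2 units: 7.8 − 6 × 0.15 = 6.90 on day 7, transfused to 8.90, then 8.75, 8.60, 8.45, 8.30. Recorded time: day 7.
- Trigger 7.0, 1 unit: 6.90 becomes 7.90 on day 7, and hemoglobin never exceeds 8. Not met in 28 days.

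A patient whose hemoglobin is 9.0 at first dose because of earlier transfusion meets the rule on day 1 with no transfusion on drug: 9.0 − 4 × 0.20 = 8.2 on the fifth day, even at the fastest assumed fall.

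**Does a five-day untransfused condition suffice?**

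Only partly. In the second case above, days 8 to 12 are untransfused at 8.75, 8.60, 8.45, 8.30 and 8.15, so the date only moves from day 7 to day 8. A 14-day run needs a first-day value above 8 + 13d, that is 9.3 to 10.6; at d = 0.15 it needs more than 9.95, which this patient does not reach. The longer run is not immune. With trigger 8.0, 2 units and d = 0.10, the value on the day after transfusion is at least 8.0 − 0.1 + 2 − 0.1 = 9.8, above the 9.3 needed.

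**The case against.** The strongest reply is that item 3 does not rest on the hemoglobin time alone. It also lists a rate of independence and an erythroid response that takes transfusion into account in both limbs. The list is worded as inclusive, section 2.2 itself names the time measure, and section 12 has a method for time-to-event data. This stands to a point: the objective is under-defined rather than abandoned, and a reader who inferred that nothing in the plan addresses it would be wrong. But none of the listed items is a time to independence, none defines independence, and the erythroid response is a yes/no outcome limited to patients below 8 g/dL at baseline.

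A second reply is that the documents give no red-cell trigger. This also stands. It rules out saying that the hemoglobin time simply measures transfusion practice or that its median will be near zero; under the most restrictive assumption above, transfusion alone never meets the rule.

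A reader might also infer that the window for the independence rate is too short. The documents do not support that. IC day 28 leaves 14, 12 or 4 days after a first dose on day 14, 16 or 24. However, the rate runs on an IC clock, and nothing requires the transfusion-free run to begin after dosing. The two-week span in item 3 belongs to the erythroid response. Four weeks counted from the end of IC (day 7) would close on day 35 and leave 21, 19 or 11 days. The 4-day case uses only one of two timing rules in section 4.1: five business days after a day-17 marrow reaches about day 24, while a 7- to 9-day gap after IC gives days 14 to 16.

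**Conclusion.** The point holds in two parts. From the text alone: objective 2.2.3 has no matching endpoint, red-cell transfusion independence is undefined, and the hemoglobin time lacks the untransfused condition that comparable rules in section 10.2 carry. From the illustration: that time can be met with no marrow recovery and is confounded by transfusion practice. Its size cannot be fixed from the documents; under the assumed inputs the same non-recovering patient is recorded anywhere from day 1 to never in 28 days.

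The consequence is limited. This is a secondary, exploratory measure. The go/no-go rule, the primary platelet endpoint and the sample size of 31 do not depend on it. It should be corrected because, followed as written, the rule can give a misleading recovery time.

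**What to change.** In section 10.2, item 3:

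1. Define red-cell transfusion independence as the first day of a prespecified run with no red-cell transfusion and hemoglobin above 8 g/dL on the counts taken. The two-week span already used in item 3 is one option and is less open to carry-over than five days. State how the run is judged when outpatient counts are weekly.
2. Report time to independence from IC day 1 by Kaplan-Meier. Censor at the start of post-remission therapy or last follow-up, and do not count death before independence as recovery. Scoring patients who move to post-remission therapy as failures would penalise early recoverers and run against section 10.1.2, which can count that transition as a complete platelet response. Report how many are censored this way, since that censoring may be related to recovery.
3. Use the same definition for the independence rate, and state whether the four weeks run from the start or the end of IC.
4. Add the no-transfusion condition to the hemoglobin time or label it descriptive. With a five-day run, some carry-over remains.

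The cost is mainly wording. Times will be longer and more heavily censored. Section 8.2, item 7, records transfusion dates while on drug, and calendar note d refers to the hospital stay. Red-cell transfusion dates must therefore be captured through short-term follow-up under section 8.3, item 7, for the run to be confirmed.

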## 11.0 ADVERSE EVENTS

The investigator or site staff will be responsible for detecting, documenting and reporting events that meet the definition of an adverse events (AE) or severe adverse events (SAE).

### 11.1 Definition of an AE

Any untoward medical occurrence in a subject or clinical investigation subject, temporally associated with the use of a medicinal product, whether or not considered related to the medicinal product.

Note: An AE can therefore be any unfavorable and unintended sign (including an abnormal laboratory finding), symptom, or disease (new or exacerbated) temporally associated with the use of a medicinal product.

Events meeting the definition of an AE include:

- Exacerbation of a chronic or intermittent pre-existing condition including either an increase in frequency and/or intensity of the condition
- New conditions detected or diagnosed after investigational product administration even though it may have been present prior to the start of the study
- Signs, symptoms, or the clinical sequelae of a suspected interaction
- Signs, symptoms, or the clinical sequelae of a suspected overdose of either investigational product or a concomitant medication (overdose per se will not be reported as an AE/SAE).

“Lack of efficacy” or “failure of expected pharmacological action” per se will not be reported as an AE or SAE. However, the signs and symptoms and/or clinical sequelae resulting from lack of efficacy will be reported if they fulfill the definition of an AE or SAE.

Events that do not meet the definition of an AE include:

- Medical or surgical procedures (e.g., endoscopy, appendectomy); the condition that leads to the procedure is an AE.
- Situations where an untoward medical occurrence did not occur (social and/or convenience admission to a hospital)
- Anticipated day-to-day fluctuations of pre-existing disease(s) or condition(s) present or detected at the start of the study that do not worsen

- The disease/disorder being studied or expected progression, signs, or symptoms of the disease/disorder being studied, unless more severe than expected for the subject's condition. This includes hematologic abnormalities, as these will be related to the disease and/or the IC.

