### 3.2 Exclusion Criteria

1. Any serious medical condition, laboratory abnormality, or psychiatric illness that, in the view of the treating physician, would place the participant at an unacceptable risk if he or she were to participate in the study or would prevent that person from giving informed consent.
2. Any active malignancy (unrelated, non-hematological malignancy) diagnosed within the past 12 months of starting the study drug (other than curatively treated carcinoma-in-situ of the cervix or non-melanoma skin cancer).
3. Secondary AML arising out of myeloproliferative neoplasms [as per the revised 2008 WHO classification of myeloid neoplasms and acute leukemias] and MDS/MPD neoplasms other than CMML [as per the revised 2008 WHO classification of myeloid neoplasms and acute leukemias]. Refractory Anemia with Ringed Sideroblasts with thrombocytosis (RARS-T) classified as MDS/MPN neoplasm, unclassifiable will be excluded. AML patients with presenting features suspicious of underlying unrecognized MPD such as marked splenomegaly ( $\geq 20$  cm) and thrombocytosis ( $>400,000$  per microliter) will be excluded. Patients with relapsed or refractory AML will be excluded.
4. Radiation therapy, cytotoxic chemotherapy, and combined modality (both radiation and chemotherapy) used to treat other cancers or medical conditions and administered within 6 months prior to study enrollment. Use of hydroxyurea or emergent leukapheresis (for cytoreduction of highly elevated white blood cell counts) is permissible. Those AML patients who initially receive treatment with all-trans retinoic acid (ATRA) for presumptive diagnosis of APL but if APL is ruled out in final pathology will be eligible for the study.
5. Prior history of treatment with recombinant TPO or TPO-R agonists.
6. History of arterial or venous thrombosis [excluding line-thrombosis] within the last 1 year, or those with known inherited coagulopathies. Arterial or venous thrombosis includes pulmonary embolism, deep vein thrombosis of both upper [excluding line-thrombosis] and lower extremities, coronary artery disease managed medically or requiring intervention (percutaneous stent placement or coronary bypass surgery), cerebrovascular accident (for transient ischemic attacks clinical documentation is required), or involvement of other organs (such as hepatic, renal, spleen or other sites).
7. Any evidence of fibrosis on morphological examination of bone marrow at the time of AML diagnosis.

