#### 6.5 Bone Marrow Reticulin Formation and Risk of Bone Marrow Fibrosis

Thrombopoietin (TPO) receptor agonists, including eltrombopag, may increase the risk for development or progression of reticulin fibrosis within the bone marrow. Baseline information on bone marrow reticulin fibrosis is routinely obtained as part of bone marrow evaluation at the time of AML diagnosis at Cleveland Clinic. Prior to initiation of study medication, the peripheral blood smear will be examined to establish a baseline level of cellular morphologic abnormalities.

A follow up peripheral blood and bone marrow smear for any new or worsening morphological abnormalities (e.g., teardrop and nucleated red blood cells, immature white blood cells) will be performed at 6 week time point (from IC) when the remission status is routinely assessed (i.e. day ~30-45 bone marrow). If any new abnormalities are detected, additional bone marrow biopsies will be performed at periodic intervals based on clinical judgment.

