## 8.0 CLINICAL MONITORING

### 8.1 Pre-induction Evaluation

Screening evaluation must be completed before starting remission IC and should include the following:

- 1) A signed informed consent.
- 2) Relevant medical history, including a detailed history for any antecedent hematologic disorder (AHD) and all treatments used for AHD including cytotoxic chemotherapy, radiation, or combined modality therapy. Review of all medications used during the 4-week period prior to screening date will be done.
- 3) CBC with differential at the time of diagnostic bone marrow biopsy for confirmation of AML. Documentation of all transfusions (red blood cells and platelets) along with dates of transfusion dating back to 8-weeks from the date of screening.
- 4) Physical examination and vital signs, including measurement of blood pressure, pulse, respiratory rate, pulse oximetry (oxygen saturation), height and body weight.
- 5) Assessment of ECOG performance status.
- 6) Documentation of AML classification according to the revised WHO 2008 classification.
- 7) Peripheral blood smear.
- 8) Bone marrow aspiration and biopsy for the following studies: cytologic analysis; morphologic assessment; flow cytometry assessment of marrow aspirate; CD34 immunostaining where necessary to enumerate marrow myeloblasts; metaphase cytogenetics; mutational analysis (especially c-kit mutations in favorable risk AML and NPM1, FLT3 and CEBPA mutations in patients with normal cytogenetics); and assessment of bone marrow fibrosis with reticulin and collagen staining. All these tests are currently done as routine standard of care. The results of mutational studies and metaphase cytogenetics are not necessary for starting patient on the study drug.
- 9) Comprehensive metabolic panel evaluations, including blood glucose, total protein, albumin, creatinine, blood urea nitrogen (BUN), serum bicarbonate ( $\text{CO}_2$ ), calcium, phosphorus, sodium, potassium, chloride, aspartate aminotransferase (AST), alanine aminotransferase (ALT), total bilirubin and alkaline phosphatase.
- 10) Remote hepatitis panel. ELISA for HIV.

- 11) A 12-lead electrocardiogram (ECG), following at least a 5-minute rest in supine position.
- 12) Baseline ophthalmological examination to be performed only in those presenting with new symptoms of visual impairment or insufficiency at the time of diagnosis of AML or those with known ocular conditions with accompanying vision defects.

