k. **Bone marrow biopsy:** Bone marrow evaluation will include cellularity analysis, morphological assessment of all three cell lineages, assessment of blast percentage, fibrosis and metaphase cytogenetics. Tests for molecular mutations and FISH studies will be done as necessary as part of standard of care where indicated. **D14-17** denotes marrow evaluation between day 14 to 17 from the start date of IC to check for persistent disease. **D30-45** denotes marrow evaluation typically between day 30 to 45 from the start date of IC to check for remission status or refractory disease. The need for additional bone marrow biopsies including end of study bone marrow biopsy will be determined clinically based on peripheral blood count abnormalities or morphology

l: **Ophthalmologic evaluation:** Complaints of any new or recent onset visual symptoms at the time of AML diagnosis. Those with known prior or existing ocular conditions such as any vitreoretinal diseases, age-related macular degeneration, optic nerve disease, glaucoma and corneal diseases as well as patients in whom there is clinical suspicion of cataracts will be evaluated at baseline. A follow up exam will be done at 2 months after stopping the drug if clinically indicated.

m: A 12-lead ECG will be obtained for each patient at screening (baseline). A pre- and post-dose 12-lead ECG will be performed on the first day of eltrombopag administration. The post-dose ECG is to be performed within a 2-4 hour window post-dose (preferably within 3 hours after administration of study drug). Thereafter, 12 lead ECGs will be performed as clinically indicated.

n: Adverse events that are related to the study drug (eltrombopag) will be followed through resolution or stabilization.

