### **11.4 Laboratory and Other Safety Assessment Abnormalities Reported as AEs and SAEs**

Any abnormal laboratory test results (clinical chemistry, or urinalysis) or other safety assessments (e.g., ECGs, radiological scans, vital signs measurements), including those that worsen from baseline, and felt to be clinically significant in the medical and scientific judgment of the investigator are to be recorded as AEs or SAEs.0, with the exception of hematologic AEs.

However, any clinically significant safety assessments that are associated with the underlying disease or with IC are not to be reported as AEs or SAEs, except for findings judged by the investigator to be more severe than expected for the subject’s condition or death.

Data will be collected for typical disease-related events such as anemia, leucopenia, worsening of thrombocytopenia or infections. All events of possible drug-induced liver injury with hyperbilirubinemia (defined as ALT  $\geq 2.5 \times$  ULN plus bilirubin  $\geq 2 \times$  ULN and/or INR  $> 1.5$  or ALT  $\geq 2.5 \times$  ULN) require reporting as an SAE. Bilirubin fractionation is performed if testing is available. If testing is unavailable and a subject meets the criterion of total bilirubin  $\geq 2 \times$  ULN, then the event is still reported as an SAE. If INR is obtained, include values on the SAE form. INR elevations  $> 1.5$  suggest severe liver injury.

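### New marrow fibrosis is a named eltrombopag risk, but the adverse event rules leave its status unclear, so it need not appear in the safety results

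*Combined protocol and SAP*

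**What the plan says.** **The risk.** Section 6.5 says that drugs of this class, eltrombopag included, "may increase the risk for development or progression of reticulin fibrosis within the bone marrow".

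**What is read.**
- Section 3.2, exclusion 7, bars "Any evidence of fibrosis on morphological examination of bone marrow at the time of AML diagnosis".
- Section 8.1, item 8, requires "assessment of bone marrow fibrosis with reticulin and collagen staining" before induction.
- Note k to the calendar in 8.4 covers the pre-induction, day 14-17 and day 30-45 marrows and lists "assessment of blast percentage, fibrosis and metaphase cytogenetics".
- Section 6.5 describes the later check differently: "A follow up peripheral blood and bone marrow smear for any new or worsening morphological abnormalities".
- On a new finding, 6.5 says: "If any new abnormalities are detected, additional bone marrow biopsies will be performed at periodic intervals based on clinical judgment". It names no reporting step.

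**What is reported.** Section 10.2(5) evaluates safety by how often adverse events occur and how severe they are. Neither Section 10 nor Section 12.0 mentions fibrosis.

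**What is excluded.** Section 11.1 ends its list of events that are not adverse events with "This includes hematologic abnormalities, as these will be related to the disease and/or the IC". Section 11.4 has clinically significant laboratory and other findings recorded "with the exception of hematologic AEs". Section 11.2, items g and h, keeps serious hematologic events out of the SAE definition. Item h makes one exception, for unprovoked thromboembolism.

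**The concern.** The trial names a drug-specific harm, examines marrows for it, and then sends all safety reporting through a definition that may remove it. The stated ground for removal is that hematologic findings come from the leukemia or the induction. For a harm the protocol attributes to the drug class, that cause cannot be assumed in advance.

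At stake is how the safety report can be read. If fibrosis may be reported or left out at a site's discretion, an adverse event table without it could mean that no marrow showed fibrosis or that nobody recorded it. The question has some weight here: Section 7.2 describes experience in chemotherapy-induced thrombocytopenia at 100 mg or less, while this trial starts most patients at 200 mg.

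**Working it through.** **1. Where could a case of new fibrosis appear?**
- Primary endpoint and response definitions (10.1): platelet counts only.
- Secondary endpoints (10.2): platelet, neutrophil and red cell recovery, subgroups, disease outcomes, survival and safety through adverse events. Fibrosis is not listed.
- Section 12.0: no fibrosis summary.
- Adverse event listing: only if the event qualifies under Section 11.

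**2. Does it qualify under Section 11?**
- *Against:* 11.1, 11.2(g), 11.2(h) and 11.4 all set hematologic events aside.
- *For:* 11.1 counts conditions first found after the drug is given. It also exempts from the exclusion anything worse than the patient's condition would predict, and 11.4 has a similar exemption. Section 11.5 drops its listed events only when they are not attributed to study drug.
- *Unresolved:* nothing says whether marrow fibrosis is a hematologic abnormality. The 11.5 list covers progression, cytopenias and infections, not fibrosis.

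Two readers could therefore code the same pathology report differently and both follow the protocol.

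**3. Do the other Section 6 risks have a route into the results?**
- Liver injury: compulsory SAE reporting (11.4).
- Thromboembolism: exception in 11.2(h).
- Bleeding: clinically significant bleeding endpoint (10.2(1)).
- Disease progression: refractory disease and survival (10.2(5)).
- Ocular symptoms: documented as an adverse effect (6.7).
- QT prolongation: ECG findings recorded under 11.4.
- Fibrosis: none assured.

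**4. The plan's own safety figures.** Section 12.0 gives, for n = 31, a 95% interval half-width of at most 18% and a chance of at least 80% of seeing one or more events at 5% risk.
- 1 − 0.95^31 = 79.6%, which agrees after rounding.
- 1.96 × √(0.25/31) = 17.6%, which agrees. The exact interval at 15 or 16 of 31 has half-width 18.4%.

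These figures assume that every event is recorded. If only a fraction c of cases is recorded (an assumption; the documents give no value), the chance of seeing at least one at 5% risk is 1 − (1 − 0.05c)^31:

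| c | Chance of at least one recorded case |
|---|---|
| 1 | 80% |
| 0.5 | 1 − 0.975^31 = 54% |
| 0 | 0% |

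**5. What a table would deliver.** With zero cases among n assessable marrows, the exact two-sided 95% upper limit is 1 − 0.025^(1/n).

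| Result | Limit or interval |
|---|---|
| 0/31 | upper limit 11.2% (9.2% one-sided) |
| 0/25 (assumed count) | upper limit 13.7% |
| 0/20 (assumed count) | upper limit 16.8% |
| 0/12 (stop after stage 1) | upper limit 26.5% |
| 1/31 | 0.1% to 16.7% |

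The chance of at least one case among 31 is 27%, 47%, 80% and 96% at true risks of 1%, 2%, 5% and 10%.

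**The case against.** The best defence is that Section 11 does not exclude fibrosis. The sentence in 11.1 closes an item about the disease under study and its expected signs. The disease-related examples elsewhere in Section 11 are low counts, infections and progression. Since any fibrosis at diagnosis bars entry, later fibrosis is new since diagnosis and fits the rule on newly found conditions. Section 12.0 also already offers a confidence interval for any type of toxicity.

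Much of this stands. A reader might infer that the plan classes new fibrosis as not an adverse event. The documents do not support that: a site may report it, and several clauses would justify doing so. But a permitted report is not a required one. The interval in 12.0 helps only once a case is recorded.

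A reader might also infer that exclusion 7 makes every later case a drug effect. It does not. The exclusion looks at the marrow at diagnosis, before induction, so fibrosis could be present before the first dose. The day 14-17 marrow is the only scheduled reading after induction and before drug.

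Finally, a reader might try to fix the day of treatment on which the follow-up marrow falls. Section 4.1 gives two start windows that need not agree: within 5 business days of the day 14-17 marrow, and 7-9 days after induction ends. Section 6.5 speaks of six weeks as well as roughly day 30-45, and 7.3 ends treatment early on platelet response. No single exposure range follows, so actual days on drug should be reported.

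**Conclusion.** The point holds as an ambiguity with a practical consequence. A stated rule, repeated across Section 11, allows a named drug risk to drop out of the only safety output, while other clauses would keep it in. Reporting is left to judgment, so silence cannot be read as absence.

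The size is the difference between no interpretable statement about fibrosis and, for 0 of 31, an upper limit of 11.2%. That limit assumes full accrual and 31 assessable marrows; fewer would widen it. The primary endpoint and the two-stage decision rule are unaffected.

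A second gap is smaller. Reticulin and collagen staining is named only before induction, note k gives no stain or grade, and 6.5 speaks of a smear. How firmly later marrows would detect fibrosis is therefore uncertain. Section 8.3 does schedule an aspirate and biopsy around day 30-45, so a specimen should exist.

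**What to change.** - **Sections 11.1, 11.2 and 11.4, reconciled with 11.5:** state that new or increased marrow reticulin or collagen fibrosis is recorded as an adverse event regardless of the hematologic exclusion. Item h of 11.2 already makes an exception of this kind for thromboembolism among SAEs.
- **Sections 10.2(5) and 12.0:** add one table with the number and proportion of treated patients showing fibrosis at the day 30-45 marrow and at any later standard-care marrow. Give the exact 95% interval, with assessable marrows as denominator. Show each patient's day 14-17 reading as comparator where available, and days of eltrombopag taken before the marrow.
- **Section 6.5 and note k:** reconcile the smear with the marrow evaluation, and state how marrows after baseline are read for fibrosis, including stain and grade.

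The cost is wording changes and one table from pathology reports on marrows already scheduled. No extra biopsy is needed, although stating a stain may mean additional staining of specimens already taken. The downside is limited interpretability: day 30-45 readings are confounded by recent induction, some marrows may not be assessable, and with no control arm the table describes frequency without establishing cause. A footnote should say so.
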